9.4.15 Work Instability Scale for Rheumatoid Arthritis (RA-WIS)

The 23-item RA-WIS is a simple validated tool to evaluate work instability (the consequence of a mismatch between an individual's functional ability and their work

tasks). It can be self-administered by the patients. To calculate the RA-WIS scale, one can simply add up the number of "true" responses. If the scale is < 10, it means low risk and no action is needed. If the scale is between 10 and 17, it means medium risk and appropriate advice and information should be given. If the scale is > 17, it means high risk and it could warrant referral.

10.0 Safety Analysis

10.1 General Considerations

Safety analyses will be carried out using the Safety Analysis Set. There are two sets of planned safety analysis: safety analysis for Period 1, and long-term safety analysis.

Safety Analysis for Period 1

Standard safety analysis by the "as treated" treatment groups of Upadacitinib 7.5 mg QD, Upadacitinib 15 mg QD, Upadacitinib 30 mg QD, and combined placebo groups will be performed on safety data in Period 1. No protocol-defined treatment switching will occur prior to the end of Period 1.

The standard safety analyses will include reporting of adverse events (AEs), laboratory, and vital signs measurements. Frequency tables of subjects with treatment-emergent adverse events (TEAEs) by system organ class (SOC) and by preferred term (PT) as in the Medical Dictionary for Regulatory Activities (MedDRA) dictionary will be provided by treatment group. Mean changes from baseline in all continuous laboratory parameters and vital signs variables at each visit will be summarized by "as treated" treatment group. Frequency tables of subjects meeting criteria for potentially clinically significant vital sign values and for potentially clinically significant laboratory values will be provided by treatment group. Missing safety data will not be imputed.

Long Term Safety Analysis

Long term safety analyses that account for protocol-defined treatment switching include reporting of AE rate adjusted by cumulative exposure, mean change from baseline in

laboratory parameters and vital sign variables, and rate of potentially clinically significant laboratory and vital signs values. The treatment-emergent adverse event (TEAE) rate per 100 patient-years of exposure will be presented by actual treatment received at the time of AE (as described in Section 10.2.2.2). Listing of subjects with TEAEs by SOC and PT will be provided. Mean changes from baseline in all continuous laboratory parameters and vital signs variables at each visit will be summarized by "as treated" treatment group sequences defined as follows (as described in Section 10.3.3 and Section 10.4.3). Frequency tables and listings of subjects meeting criteria for potentially clinically significant vital sign values and for potentially clinically significant laboratory values will be provided by actual treatment received at the time of event. Missing safety data will not be imputed.

"As treated" treatment group sequences:

1. Upadacitinib (ABT-494) 7.5 mg QD
2. Upadacitinib (ABT-494) 15 mg QD
3. Upadacitinib (ABT-494) 30 mg QD
4. Placebo → Upadacitinib (ABT-494) 7.5 mg QD
5. Placebo → Upadacitinib (ABT-494) 15 mg QD
6. Placebo → Upadacitinib (ABT-494) 30 mg QD

10.2 Analysis of Adverse Events

10.2.1 Treatment-Emergent Adverse Events

A treatment-emergent Adverse Event (TEAE) is defined as an adverse event with an onset date that is after the first dose of study drug, and no more than 30 days of the drug after the last dose of study drug.

Events where the onset date is the same as the study drug start date are assumed to be treatment-emergent, unless the study drug start time and the adverse event start time are

collected and the adverse event start time is prior to the study drug start time. If an incomplete onset date was collected for an adverse event, the event will be assumed to be treatment-emergent unless there is other evidence that confirms that the event was not treatment-emergent (e.g., the event end date was prior to the study drug start date).

Adverse event data will be presented by SOCs and PTs using MedDRA version 19.0 or most up to date version. All adverse event tables will be sorted in alphabetical order by SOC and PT and descending percentages for each treatment group.

10.2.2 Analysis of Adverse Events for Period 1

10.2.2.1 Adverse Events Overview

The number and percentage of subjects experiencing TEAEs will be summarized by "as treated" treatment group and overall for the following AE categories.

- All TEAEs
- Treatment-emergent serious adverse events (SAEs)
- Treatment-emergent severe adverse events
- TEAEs reasonably possibly related to study drug
- TEAEs of special interest
- TEAEs leading to discontinuation of study drug
- TEAE leading to death

Additional AEs may be considered for tabulation/summary based on recommendations from Clinical and Safety as deemed appropriate.

For TEAEs of special interest, the point estimate and 95% CI (using normal approximation) will be provided for the treatment difference in AE percentage between each Upadacitinib dose group and the combined placebo group.

10.2.2.2 Adverse Events by System Organ Class and Preferred Term

The number and percentage of subjects experiencing adverse events will be tabulated by SOC and MedDRA PT by "as treated" treatment group and overall. The SOCs will be presented in alphabetical order, and the PTs will be presented in alphabetical order within each SOC.

The following summaries of adverse events will be generated:

- All TEAEs
- Treatment-emergent serious adverse events (SAEs)
- Treatment-emergent severe adverse events
- TEAEs reasonably possibly related to study drug
- TEAEs leading to discontinuation of study drug
- TEAE leading to death
- Frequent AEs (reported in 5% of subjects or more in any treatment group)
- TEAEs of special interest

Subjects reporting more than one adverse event for a given MedDRA preferred term will be counted only once for that term (most severe incident for the severity tables and most related incident for the relationship tables). Subjects reporting more than one type of adverse event within a SOC will be counted only once for that SOC. Subjects reporting more than one type of adverse event will be counted only once in the overall total.

10.2.2.3 TEAEs by Maximum Severity

TEAEs will also be summarized by maximum severity by "as treated" treatment group and overall. If a subject has an AE with an unknown severity, then the subject will be counted in the severity category of unknown, even if the subject has another occurrence of the same event with a severity present. The only exception is that if the subject has another occurrence of the same AE with the most extreme severity – severe. In this case, the subject will be counted under the severe category.

10.2.2.4 TEAEs by Relationship

TEAEs will also be summarized by relationship to Upadacitinib and Placebo, as assessed by the investigator, by "as treated" treatment group and overall. If a subject has a TEAE with an unknown relationship, then the subject will be counted in the relationship category of "unknown," even if the subject has another occurrence of the same event with a relationship present. The only exception is if the subject has another occurrence of the same TEAE with a relationship assessment of "reasonable possibility." In this case, the subject will be counted under the "reasonable possibility" category.

10.2.2.5 Frequent ($\geq 5\%$) Adverse Events and Reasonably Possibly Related Adverse Events by System Organ Class and Preferred Term

TEAEs and reasonably possibly related AEs occurring for more than 5% of the subjects in any of the "as treated" treatment groups will be summarized by MedDRA PT in decreasing frequency separately.

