### **6.1.3 Relationship to Study Drug**

The Investigator will use the following definitions to assess the relationship of the AE to the use of study drug:

Reasonable Possibility	After consideration of factors including timing of the event, biologic plausibility, clinical judgment, and potential alternative causes, there is sufficient evidence (information) to suggest a causal relationship.
No Reasonable Possibility	After consideration of factors including timing of the event, biologic plausibility, clinical judgment, and potential alternative causes, there is insufficient evidence (information) to suggest a causal relationship.

[figure not shown]
For causality assessments, events assessed as having a reasonable possibility of being related to the study drug will be considered "associated." Events assessed as having no reasonable possibility of being related to study drug will be considered "not associated." In addition, when the investigator has not reported a relationship or deemed it not assessable, AbbVie will consider the event associated.

If an Investigator's opinion of no reasonable possibility of being related to study drug is given, an Other cause of event must be provided by the investigator for the serious adverse event.

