### **8.1.5            Safety Analyses**

#### **8.1.5.1            General Considerations**

Safety analyses will be carried out using the Safety Analysis Set. Analyses will be conducted for Period 1 alone, as well as for Period 1 and Period 2 combined. Safety analyses are based on treatments actually received. Safety will be assessed by AEs, physical examination, laboratory assessments, ECG, and vital signs. Frequency tables and lists of subjects with treatment-emergent AEs by preferred term as in the Medical Dictionary for Regulatory Activities (MedDRA) dictionary, by system organ class, by severity, and by relationship to the study drug as assessed by the Investigator will be provided. The changes from baseline in vital signs, physical examination results, and clinical laboratory values will be analyzed in a descriptive manner. Shift of laboratory values from baseline to defined time points will be tabulated.

Missing safety data will not be imputed.

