### **8.1.5.2.1 Treatment-Emergent Adverse Events (TEAE)**

AEs will be coded using MedDRA. A TEAE is defined as AE that began or worsened in severity after initiation of study drug.

AEs starting more than 30 days following the last dose of study drug will not be included in summaries of TEAEs. For subjects who continued into Period 2, the AEs that are reported in Period 2 will be captured in the combined safety analysis of Period 1 and Period 2.

As a general safety summary, the number and percentage of subjects experiencing TEAEs will be summarized for each treatment group for the following AE categories:

- All AEs;
- All severe AEs;
- All reasonably possibly related AEs;
- All SAEs;
- Frequent AEs (reported in 5% of subjects or more in any treatment group);
- Frequent reasonably possibly related AEs (reported in 5% of subjects or more in any treatment group);
- Discontinuations due to AEs;
- Death.

Additional AEs may be considered for tabulation/summary based on recommendations from Clinical and Safety as deemed appropriate.

TEAEs will be summarized and presented by system organ classes (SOCs) and preferred terms (PTs) using MedDRA. The SOCs will be presented in alphabetical order, and the PTs will be presented in alphabetical order within each SOC.

TEAE will also be summarized by maximum severity and by maximum relationship.

The AEs of special interest (including but not limited to serious infection, opportunistic infection, malignancy, non-melanoma skin cancer (NMSC), malignancy other than NMSC, lymphoma, hepatic disorder, gastrointestinal perforation, anemia, neutropenia, lymphopenia, herpes zoster, increased CPK, renal dysfunction, tuberculosis, adjudicated cardiovascular events and embolic and thrombotic events (non-cardiac, non-CNS) will be summarized. Event rate (per 100 patient years) for AEs of special interest will also be summarized for the combined safety analysis of Period 1 and Period 2.

All AEs leading to discontinuation of study drug will be presented in listing format. A listing by treatment group of TEAEs grouped by SOC and MedDRA preferred term with subject identification numbers will be generated.

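### SAP 10.2.2.4 puts adverse events with no causality assessment in an 'unknown' class, where protocol 6.1.3 treats them as associated; the other related-event outputs state no rule

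*SAP*

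**What the plan says.** Protocol 6.1.3 gives the investigator two causality categories, 'reasonable possibility' and 'no reasonable possibility'. It links the first to the sponsor's term: "events assessed as having a reasonable possibility of being related to the study drug will be considered" 'associated'. It then covers the case with no usable assessment: "when the investigator has not reported a relationship or deemed it not assessable, AbbVie will consider the event associated". Protocol 8.1.5.2.1 adds that "TEAE will also be summarized by maximum severity and by maximum relationship", and mentions no unknown class.

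SAP 10.2.2.4 sets a different rule for the Period 1 by-relationship table: "If a subject has a TEAE with an unknown relationship, then the subject will be counted in the relationship category of" 'unknown'. This applies even when another occurrence of the same event has been assessed. There is one way out: "The only exception is if the subject has another occurrence of the same TEAE with a relationship assessment of" 'reasonable possibility'.

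Related TEAEs are also reported in SAP 10.2.2.1 (overview), 10.2.2.2 (by SOC and PT), 10.2.2.5 (frequent related events), 10.2.3.1 and 10.2.3.2 (long-term rates). Each has a row or table for related events, in the overview worded "TEAEs reasonably possibly related to study drug". None of them says what happens when the relationship is missing.

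**The concern.** The same event could be associated under the protocol and 'unknown' in the SAP's table. SAP section 3.0 presents the SAP as elaborating the protocol's methods, and the SAP declares no departure on this point. At stake is whether the related-event counts agree with the sponsor's own causality rule, and whether the remaining related-event outputs can be programmed in only one way. As written, one programmer could select only events marked 'reasonable possibility', and another could apply protocol 6.1.3. Both would be following the plan.

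**Working it through.** There is no plan figure to reproduce. The check is a comparison of two rules, followed by simple division for scale.

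**Step 1: the two rules side by side.** Take one subject's assessments of the same TEAE in Period 1.

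| Assessments recorded | SAP 10.2.2.4 | Protocol 6.1.3 | Differ? |
|---|---|---|---|
| Unknown only | Unknown | Associated | Yes |
| Unknown and 'no reasonable possibility' | Unknown | Associated | Yes |
| Unknown and 'reasonable possibility' | Reasonable possibility | Associated | No |
| No unknown | As assessed | As assessed | No |

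In the first two patterns the SAP gives the lower related count. In no pattern does it give the higher one.

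**Step 2: is this a version effect?** SAP Version 1.0 is dated 31 August 2017 and the current protocol synopsis 23 February 2018. For section 6.1.3, protocol Appendix O lists changes to the two category definitions and to the first sentence of the following paragraph. It lists no change to the sentence on unreported or non-assessable relationship. The mismatch is therefore not explained by that amendment.

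**Step 3: scale in Period 1.** The planned group size is 48 per upadacitinib dose. The combined placebo group is 3 × 16 = 48 (protocol 5.1 and 8.1.4.1). Let k be the number of subjects in a group who have an unknown assessment and no related assessment at the level being tabulated. The protocol rule then raises that group's related percentage by k/48:

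- k = 0: no change
- k = 1: 1/48 = 2.1 points
- k = 2: 2/48 = 4.2 points
- k = 3: 3/48 = 6.3 points

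**Step 4: the frequent related-event table.** The cut-off is 5% in any group. The heading of SAP 10.2.2.5 and protocol 8.1.5.2.1 read it as 5% or more, and the text of SAP 10.2.2.5 as more than 5%. Either way, 2/48 = 4.2% is not listed and 3/48 = 6.3% is. One reclassified subject can therefore decide whether a preferred term appears, if that table also leaves unknowns out of the related count. The SAP does not say whether it does.

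**Step 5: long-term rates.** SAP 10.2.3.1 and 10.2.3.2 count events, not subjects, per 100 patient-years of exposure. The 1/48 step does not carry over to them.

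**The case against.** The best defence is that the relationship tables report the investigator's view. The protocol says so in 8.1.5.1 ("by relationship to the study drug as assessed by the Investigator will be provided"), and so does the SAP ("TEAEs will also be summarized by relationship to Upadacitinib and Placebo, as assessed by the investigator"). On this reading the sponsor's default in 6.1.3 belongs to event handling, and a table that shows missing assessments in their own row can stand beside it. Part of this stands: 6.1.3 does not say that its default governs the statistical tables, and an 'unknown' row does not hide anyone. It does not settle the matter, because the default covers exactly the events for which no investigator assessment exists. If the default was meant to stay out of the tables, the SAP needed to say so.

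Three stronger readings are tempting, and the documents do not support them.

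- A reader might infer that every related-event table undercounts. The 'unknown' rule is written for one table only. The other outputs are silent, which is a gap and not a stated undercount.
- A reader might infer that the rule always flatters the drug. It lowers counts within any group, placebo included. Unassessed events on placebo would make upadacitinib look worse by comparison.
- A reader might infer that every unassessed event costs 2.1 points. A subject who already has a related assessment at that level is counted once in any case, so nothing moves.

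It is also fair to say that protocol 6.1 requires the investigator to record relationship for each adverse event, so missing values may be few or absent.

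**Conclusion.** The two documents state different rules for an unreported or non-assessable relationship, and the SAP neither follows the protocol rule nor explains the difference. For subjects in the first two patterns of the table, the Period 1 by-relationship summary shows fewer related cases within a group than protocol 6.1.3 gives. For the other related-TEAE outputs, the conclusion is only that no rule is stated.

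The size cannot be fixed from the documents, since the number of such events is not given. The 2.1-point step rests on the planned 48 per group and on the subject having no other related assessment at that level. The direction is certain within a group and open for comparisons between groups. These are descriptive safety summaries. The efficacy analyses and the tables of all, serious, severe, special-interest, discontinuation and fatal events are not affected. The change is worth making because related events are a required safety output and the correction is small.

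**What to change.** In SAP 10.2.2.4, replace the 'unknown' rule with the rule of protocol 6.1.3: a TEAE whose relationship is missing or not assessable is counted as 'reasonable possibility'. State that this applies to every related-TEAE summary in Period 1 and long term (10.2.2.1, 10.2.2.2, 10.2.2.4, 10.2.2.5, 10.2.3.1 and 10.2.3.2). Footnote, by treatment group, how many events were assigned this way, so that the investigator-assessed counts can still be read off.

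Keeping a separate 'unknown' row would also be workable, but only with a stated reason for departing from 6.1.3, a sensitivity table that counts those events as related, and a stated rule for the outputs that now have none.

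The cost is one SAP sentence, one derivation rule and a footnote. Related-event counts may come out slightly less favourable.

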10.2.2.6 Adverse Events of Special Interests

The Adverse Events of Special Interests (AESI) categories will be summarized and presented by "as treated" treatment group and overall using SOC and MedDRA PT. The AESI categories will be identified by the following search criteria per Standard MedDRA Queries (SMQs)/Company MedDRA Queries (CMQs) in [Table 13](#) below.

Table 13. AESI for Upadacitinib with SMQs/CMQs/PTs Searches

AESI	Type of MedDRA Query	Broad or Narrow Search	SMQ/CMQ Search Criteria
Serious Infections	CMQ		"Infections" – Subset for SAEs
Opportunistic Infection	CMQ		"Opportunistic Infection"
Malignancy	SMQ	Narrow	"Malignancies"
Non-Melanoma Skin Cancer (NMSC)	SMQ	Broad	Skin Malignant tumours (Broad SMQ) removing Melanoma CMQ
Malignancy excluding NMSC			Malignancy Narrow SMQ and removing NMSC output
Lymphoma	SMQ		"Malignant Lymphomas"
Hepatic Disorder	SMQ	Narrow	"Drug Related Hepatic Disorders"
Gastrointestinal Perforations	SMQ	Narrow	"Gastrointestinal Perforation"
Anemia	CMQ		"Non-Hemolytic and Non-Aplastic Anemias"
Neutropenia	CMQ		"Hematological Toxicity – Neutropenia"
Lymphopenia	CMQ		"Hematological Toxicity – Lymphopenia (Veliparib Product Specific)"
Herpes Zoster	CMQ		"Herpes Zoster"
Creatine Phosphokinase (CPK) Elevation	PT		Search only for the PT of "Blood creatine phosphokinase increased"
Renal Dysfunction	SMQ	Narrow	"Acute Renal, Failure"
Tuberculosis	CMQ		"Tuberculosis"
Adjudicated cardiovascular events	Output from CAC		

Additional AEs may be considered for tabulation/summary based on recommendations from Clinical and Safety as deemed appropriate.

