- Update Section **5.3.1.1**, Study Procedures, Subsection "Clinical Laboratory Tests."

**Rationale:** *Updated footnotes of Table 5 to provide clarity, additional instructions and to remain consistent with Amendment 5 changes reflected in the protocol.*

- Update Section **5.3.1.1**, Study Procedures, Subsection "Hepatitis Screen."

**Rationale:** *Updated text to clarify Hepatitis B testing requirements for HBV-DNA PCR testing. Updated text to clarify the management of subjects who develop positive result for HBV DNA PCR testing during the study,*

*including hepatologist consultation and possible study drug interruption per local guidelines.*

- Update Section 5.3.3.1.3, Additional Variables

**Rationale:** *Added change from baseline in FACIT-F and RA-WIS for all visits.*

- Update Section 5.4.1, Discontinuation of Individual Subjects.

**Rationale:** *Updated text to clarify that starting at Week 24, at least 20% improvement in both swollen joint counts and tender joint counts compared to baseline is required to remain in the study. Updated text to remove the discontinuation criterion related to the study drug interruption during the study.*

- Update Section 5.5.5.2, Identity of Investigational Product.

**Rationale:** *Updated to clarify the formulation of upadacitinib.*

- Update Section 5.5.5, Blinding of Investigational Product.

**Rationale:** *Updated text to clarify that additional unblinded analyses will be performed for the purpose of regulatory submission in addition to the one conducted after all subjects have completed Period 1 (Week 12).*

- Update Section 6.1.1.3, Adverse Events of Special Interest

**Rationale:** *Updated the adverse events of special interest that will be monitored during the study to align in content and presentation with the current version of the Product Safety Statistical Analysis Plan.*

- Update 6.1.3 Relationship to Study Drug

**Rationale:** *Updated definition for assessing the relationship of adverse events to use of study drug per sponsor guidelines.*

- Update Section 6.1.4, Adverse Event Collection Period

**Rationale:** *Updated text to implement supplemental eCRF for embolic and thrombotic events.*

- Update Section 6.1.5, Serious Adverse Event Reporting

**Rationale:** *Change the Sponsor/Emergency Contact to Dr. [REDACTED] to inform the sites of the change in contact for subject safety*

*concerns and emergencies (as per Protocol Administrative Change 4).*

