*Updated regulations governing SUSARs reporting.*

- Update Section [6.1.7](#), Toxicity Management.

**Rationale:** *Removed the requirement to discontinue subjects who experience serious infections and have interrupted study drug for more than 7 consecutive days during the first 24 weeks of the study or 30 consecutive days thereafter in order to be consistent with Section [5.4.1](#) which requires discontinuation of study drug for serious infections which cannot be adequately controlled within 14 days by anti-infective treatment. Clarified that subject should discontinue study drug for an ECG abnormality that is considered clinically significant with reasonable possibility that the event is related to study drug. Clarified that all abnormal lab tests that are considered clinically significant by the investigator should be followed to a satisfactory resolution. Updated [Table 7](#) "Specific Toxicity Management Guidelines for Abnormal Laboratory Values" to provide clarity and additional instructions for management of increased ALT/AST, Serum Creatinine and Creatine Phosphokinase.*

- Update Section [6.2.2](#), Reporting

**Rationale:** *Updated text to define Product Complaint reporting timeline as 1 business day.*

- Update Section [8.1](#) Statistical and Analytical Plans.

**Rationale:** *Updated text to clarify that additional unblinded analyses will be performed for the purpose of regulatory submission in addition to the one conducted after all subjects have completed Period 1 (Week 12).*

- Update Section [8.1.4.1.5](#) Imputation Methods.

**Rationale:** *Updated language for analysis details.*

- Update Section [8.1.5.2.1](#), Treatment-Emergent Adverse Events (TEAE)

**Rationale:** *Updated search criteria for the AEs of special interest (AESI) categories.*

- Update Section [8.1.5.3](#) Analysis of Laboratory, Vital Sign, and ECG Data.

**Rationale:** *Updated language for analysis details.*

- Update [Appendix B](#), List of Protocol Signatories.

***Rationale:*** *Updated signatories responsible for the amendment.*

- Update [Appendix N](#), Rheumatology Common Toxicity Criteria v.2.0 Example.

***Rationale:*** *Updated to clarify grading criteria for CPK and Creatinine.*

An itemized list of all changes made to the protocol under this amendment can be found in [Appendix O](#).

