### **6.1.1.3 Adverse Events of Special Interest**

The following AEs of special interest will be monitored during the study (see detailed toxicity management in Section [6.1.7](#)):

- Serious infections
- Opportunistic infections
- Herpes zoster
- Tuberculosis;
- Malignancy (all types);
- Gastrointestinal perforations;
- Adjudicated cardiovascular events (e.g., major adverse cardiovascular event [MACE]);
- Lipid profile changes;
- Anemia;
- Neutropenia;
- Lymphopenia;
- Increased serum creatinine and renal dysfunction;
- Hepatic events and increased hepatic transaminases;
- Elevated creatine phosphokinase (CPK);
- Embolic and thrombotic events (non-cardiac, non-CNS).

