3.0 Introduction

This statistical analysis plan (SAP) describes the statistical analyses to be completed by the Data and Statistical Science Department for Upadacitinib (ABT-494) Study M14-663. It provides details to further elaborate statistical methods as outlined in the protocol. Pharmacokinetic and biomarker analyses will be performed separately and reported in a separate document.

Unless noted otherwise, all analyses will be performed using SAS version 9.4 or later (SAS Institute Inc., Cary, NC 27513) under the UNIX operating system.

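### The SAP's AESI table has no row or search for embolic and thrombotic events, which the current protocol says will be summarised with rates; separately, SAP CPK Grade 1 stops at 1.5 × ULN and leaves a gap

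*SAP*

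**What the plan says.** **Protocol.** Section 8.1.5.2.1 names 17 AESI categories. The list ends: "adjudicated cardiovascular events and embolic and thrombotic events (non-cardiac, non-CNS) will be summarized". It adds, for Periods 1 and 2 combined: "Event rate (per 100 patient years) for AEs of special interest will also be summarized". Section 6.1.1.3 also lists embolic and thrombotic events for monitoring, and Section 6.1.4 assigns them a supplemental eCRF. Section 8.1.5.2.1 gives no MedDRA search for any category.

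**SAP.** Section 3.0 describes the SAP's role: "It provides details to further elaborate statistical methods as outlined in the protocol". Section 10.2.2.6 sets the identification rule, "The AESI categories will be identified by the following search criteria per Standard MedDRA Queries", and Table 13 gives each category a search or a named source. Below the table it allows that "Additional AEs may be considered for tabulation/summary based on recommendations from Clinical and Safety as deemed appropriate". Section 10.2.3.3 calculates long-term AESI rates for the categories in 10.2.2.6.

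**History.** The protocol's summary of changes (Section 1.1) explains the revised list in 6.1.1.3 as made to "align in content and presentation with the current version of the Product Safety Statistical Analysis Plan". For 8.1.5.2.1 it records: "Updated search criteria for the AEs of special interest (AESI) categories".

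**CPK.** SAP 10.3.2.2 applies NCI CTC grades to CPK in the shift tables. SAP Appendix A, row L9, ends Grade 1 at 1.5 × ULN and starts Grade 2 above 2.5 × ULN. The footnote to protocol Appendix N ends Grade 1 at 2.5 × ULN.

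**ECG.** SAP 10.5.1 names a Week 24 ECG. Note g of protocol Table 4 and note g of SAP Table 3 mention none.

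**The concern.** The protocol commits to a grouped summary and a rate for a named safety category, and the SAP is where that category should be made operational. A programmer who follows Table 13 will not produce it. The same list is the SAP's only definition of an AESI. The gap therefore reaches the AESI lines of the overview tables (10.2.2.1 and 10.2.3.1), with their differences from placebo, and the rates in 10.2.3.3.

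A grouped category depends on which preferred terms the search includes. The protocol plans further unblinded analyses for regulatory submission. If the search is chosen after treatment assignments are known, that choice is open to question. Fixing it beforehand removes the doubt.

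The CPK point is different in kind. It is a wrong number in a grading table, and programmed literally it puts some values in no grade.

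**Working it through.** **1. Category count.** I matched the list in protocol 8.1.5.2.1 to the rows of SAP Table 13.

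| Group | Protocol | SAP |
|---|---|---|
| Infections: serious, opportunistic, herpes zoster, tuberculosis | 4 | 4 |
| Neoplasms: malignancy, NMSC, malignancy without NMSC, lymphoma | 4 | 4 |
| Blood counts: anemia, neutropenia, lymphopenia | 3 | 3 |
| Hepatic, GI perforation, CPK, renal | 4 | 4 |
| Adjudicated cardiovascular | 1 | 1 |
| Embolic and thrombotic (non-cardiac, non-CNS) | 1 | 0 |
| Total | 17 | 16 |

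The difference is 17 − 16 = 1, and no SAP row lacks a protocol counterpart. The count is against 8.1.5.2.1. Section 6.1.1.3 also lists lipid changes, which are in neither 8.1.5.2.1 nor Table 13; the SAP handles lipids in its laboratory analyses.

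**2. Could another row cover it?** The adjudicated cardiovascular row takes the adjudication committee's output. The protocol lists embolic and thrombotic events separately from that category and gives them their own supplemental eCRF, apart from the MACE form. So that row does not stand in for the missing one.

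**3. What the SAP still produces.** Section 10.2.2.2 gives Period 1 counts and percentages by SOC and preferred term. Section 10.2.3.2 gives rates per 100 patient-years by SOC and preferred term, by treatment received. Section 10.2.3.4 lists serious events. What is missing is the single grouped category, as a summary and as a rate by dose.

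**4. Cause.** SAP version 1.0 is dated 31 August 2017 and the Amendment 5 synopsis 23 February 2018. Protocol Appendix O shows that Amendment 5 added the category to both 6.1.1.3 and 8.1.5.2.1. The discrepancy itself lies between the current protocol text and the SAP; the amendment history only explains it.

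**5. CPK intervals, in multiples of ULN.**

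| Grade | SAP Appendix A | Protocol Appendix N |
|---|---|---|
| 1 | above 1 to 1.5 | above 1 to 2.5 |
| 2 | above 2.5 to 5 | above 2.5 to 5 |
| 3 | above 5 to 10 | above 5 to 10 |
| 4 | above 10 | above 10 |

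The interval with no SAP grade is above 1.5 to 2.5. It is 2.5 − 1.5 = 1.0 ULN wide, out of a protocol Grade 1 interval of 2.5 − 1.0 = 1.5 ULN. Test values of 1.6, 2.0 and 2.5 × ULN get no grade under the SAP and Grade 1 under the protocol. Values of 1.2, 2.6, 5.1 and 10.1 × ULN get the same grade under both. Both the Grade 1 cells and the ungraded cells of the shift tables change. The potentially clinically significant counts in 10.3.2.3 use Grades 3 and 4, and the CPK row of Table 13 uses a preferred term, so neither moves.

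**6. ECG.** Protocol Table 4 note g starts ECGs at Week 48 and repeats them every 48 weeks, plus premature discontinuation. SAP Table 3 note g places them every 48 weeks after Week 48, which is the wording that Amendment 5 replaced (Appendix O). Neither has a Week 24 ECG, so SAP 10.5.1 disagrees with both. This rests on the notes, so the marks in the ECG rows of the tables should be checked when the text is reconciled.

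**The case against.** The strongest reply is that little is lost. The protocol requirement stands whatever the SAP leaves out, because the SAP only elaborates it. The events are collected, and dose-specific rates for each preferred term are already planned. The sentence allowing additional AEs would permit the summary. The search may also exist in the Product Safety Statistical Analysis Plan, or in a later SAP version that cannot be seen here.

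Most of this stands, and it limits the point to one grouping. It does not remove it. The permissive sentence neither commits to the category nor supplies a search. This SAP does not cite the product-level plan. Separate preferred-term rates do not give the grouped rate until someone decides which terms belong.

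On CPK, the reply is that SAP 10.3.2.2 invokes NCI CTC, so a careful programmer may correct the bound. But Appendix A labels row L9 as NCI CTC and still prints 1.5, so the SAP's own table is what would mislead.

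Three stronger readings are tempting, and the documents do not support them:

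- **Thrombotic events would go unreported.** They would not, for the reasons in step 3 of the working.
- **The SAP is out of date throughout.** It already agrees with the current protocol on the 5% threshold for frequent AEs, on FACIT-F and RA-WIS at all visits, and on graded laboratory shifts.
- **The Week 24 wording excludes later ECGs.** SAP 10.5.1 summarises by visit, so it does not.

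**Conclusion.** The point holds. SAP version 1.0 was not brought into line with Amendment 5 on the AESI list. One of 17 protocol categories has no row or search, and its grouped summary and rate by dose are missing from the SAP's planned output. This should be corrected before further unblinded analysis, but it does not threaten the trial's main conclusions.

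The CPK bound is a separate numerical error of small effect, confined to the shift tables, with Grades 2 to 4 unchanged. How many subjects fall in the ungraded interval cannot be known from the documents. The ECG wording is editorial.

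The absence of the row from this SAP is certain. A reader might infer that the programme has no search for these events at all; the documents do not show that, because the product-level plan was not available.

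**What to change.** 1. **AESI.** Before any further unblinded analysis, add a row to SAP Table 13 for embolic and thrombotic events (non-cardiac, non-CNS) with its search, or cite there the Product Safety Statistical Analysis Plan search that applies. Coverage becomes 17 of 17, and Section 10.2.3.3 picks up the rate by reference.
2. **CPK.** In SAP Appendix A, row L9, set the Grade 1 upper bound to 2.5 × ULN, as in protocol Appendix N.
3. **ECG.** Reconcile SAP 10.5.1 and SAP Table 3 note g with the current protocol schedule of activities, rather than writing a new visit list.

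The cost is a SAP amendment of a few lines: one table row or citation, one number, one sentence and one footnote. No new data are needed, since the supplemental eCRF for these events is already in the protocol.
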